6.3.1 Definition of Dose-Limiting Toxicities

A DLT is defined as any of the following events, except those that are clearly due to underlying disease or extraneous causes:

- A hematologic DLT is defined as:
 - o Grade 3 or higher event of neutropenia or thrombocytopenia, or a Grade 4 anemia, with a hypocellular bone marrow lasting for 6 weeks or more after the start of a cycle, in the absence of residual leukemia (i.e., with <5% blasts). In case of a normocellular bone marrow with <5% blasts, 8 weeks with ≥Grade 3 pancytopenia will be considered a DLT.
- A non-hematologic DLT is defined as:
 - o Grade 4 tumor lysis syndrome (Grade 3 TLS will not constitute DLT unless it leads to irreversible end-organ damage).
 - o Grade 3 or higher AE (including nausea, vomiting, diarrhea, and electrolyte imbalances lasting more than 48 hours despite optimal therapy; excluding all grades of alopecia).
 - o CTCAE Grade 3 or higher hypersensitivity reaction (regardless of premedication).
 - o CTCAE Grade 3 or higher skin ulceration.

The DLT observation period for dose-escalation will be 1 cycle.

Note: Patients who experience a DLT during Cycle 1 are to be permanently discontinued from the study.

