3.2 Dose-Escalation

In Part 1, dose-escalation will be conducted according to a 3+3 design (Figure 2). The initial dose of ADCT-402 will be 15 μ g/kg (Dose Level 1), and the highest allowed dose will be 600 μ g/kg. The potential dose levels are described in Table 1 and Table 2.

ADCT-402-102 Protocol Amendment 3

Table 1. Planned Dose Levels for ADCT-402 (Q3W Administration)

Dose Level	Dose of ADCT-402	Dose Level	Dose of ADCT-402
1	15 μg/kg	9	300 μg/kg
2	30 μg/kg	10	350 μg/kg
3	60 μg/kg	11	$400~\mu g/kg$
4	90 μg/kg	12	$450~\mu g/kg$
5	120 μg/kg	13	500 μg/kg
6	150 μg/kg	14	550 μg/kg
7	200 μg/kg	15	$600~\mu g/kg$
8	250 μg/kg		

Table 2. Planned Dose Levels for ADCT-402 (QW Administration)

Dose of ADCT-402	Dose Level	Dose of ADCT-402
5 μg/kg	7	75 μg/kg
10 μg/kg	8	100 μg/kg
20 μg/kg	9	125 μg/kg
30 μg/kg	10	150 μg/kg
40 μg/kg	11	175 μg/kg
50 μg/kg	12	200 μg/kg
	5 μg/kg 10 μg/kg 20 μg/kg 30 μg/kg 40 μg/kg	5 μg/kg 7 10 μg/kg 8 20 μg/kg 9 30 μg/kg 10 40 μg/kg 11

The dose-limiting toxicity (DLT, Section 6.3.1) observation period for dose-escalation is 1 cycle. The first patient enrolled into the study at 15 μ g/kg (Dose Level 1) must be observed for 7 days for occurrence of adverse events (AEs) prior to treating the second patient in the study. Patients will be entered sequentially to each dose level.

For each dose level, if none of the first 3 patients at that level experiences a DLT, new patients may be entered at the next higher dose level. If 1 of 3 patients experiences a DLT, up to 3 more patients are to be treated at that same dose level. If none of the additional 3 patients at that dose level experiences a DLT, new patients may then be entered at the next higher dose level. However, if 1 or more of the additional 3 patients experiences a DLT, then no further patients are to be started at that dose level and the preceding dose is identified as the MTD. The MTD;

ADCT-402-102 Protocol Amendment 3

therefore, is defined as the highest dose level at which none of the first 3 treated patients, or no more than 1 of the first 6 treated patients, experiences a DLT.

No intra-patient dose-escalation is allowed.

[figure not shown]

Figure 2. Schematic Representation for Dose-Escalation (3+3) Design

Abbreviations: DLT, dose-limiting toxicity; MTD, maximum tolerated dose; \leq , less than; \geq greater than or equal to.

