The number of dose levels will depend on the emergent toxicity profile of ADCT-402 and will be decided by the DESC (Section 6.3.2); PK, and PD evaluations may also inform decision making.

Every 3 Week (Q3W) Administration

Patients will be given ADCT-402 on Day 1 of each 3-week treatment cycle.

Weekly (QW) Administration

Patients will be given ADCT-402 QW on Days 1, 8 and 15 of each 3-week (21-day) treatment cycle.

The first dose level for the QW dosing will be based on the safety and tolerability of patients who have been treated on the every 3-week (Q3W) schedule. The first 3 patients will be given a cumulative dose each cycle that is comparable to (but not higher than) the highest dose tested at the Q3W dose schedule at which 3 patients completed the DLT observation period without a DLT. For example, if the highest Q3W dose tested at which 3 patients did not experience a DLT was cohort 150 μ g/kg, the first cohort to receive QW dosing will receive 50 μ g/kg each week for 3 weeks.

A patient will maintain the same treatment schedule throughout the duration of the trial.

ADCT-402-102 Protocol Amendment 3

Weekly dosing will be implemented at the discretion of the DESC (and in accordance with local ethics committee approvals). Once a patient achieves CR/CRi, frequency or dose may be adjusted by the DESC based on emerging safety, efficacy and PK profile.

The trial will be continuously monitored for emerging safety, efficacy and/or PK profile and the DESC will determine if it is appropriate to maintain a QW schedule, revert to a Q3W schedule, or test other dosing regimens.

During Part 1, the DESC may expand enrollment at doses below the current dose level as part of the dose-escalation process. Additional patients may only be added at a lower dose level provided there is at least 1 patient who has achieved a PR (Section 6.1) or better. No more than 10 patients in total can be treated at any dose level unless \geq 3 of the 10 patients have achieved a PR or better

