5.4 Dose Delays and Modifications

Patients will receive the first 2 cycles of ADCT-402, irrespective of blood count recovery. For patients achieving a CR/CRi, the subsequent cycle would be delayed until peripheral blood count recovery (absolute neutrophil count [ANC] $>500 \times 10^9$ /L and/or platelets $>50 \times 10^9$ /L).

The Investigator may suspend ADCT-402 dosing for up to 21 days for any patient who experiences a protocol-defined DLT after Cycle 1 (the defined DLT observation period). At the discretion of the Investigator, the dose may also be delayed for up to 21 days for any toxicity that does not meet DLT criteria. Resumption of dosing with ADCT-402 after suspension is at the discretion of the Investigator, based on assessment of the patient's clinical condition and whether or not the patient is deriving potential clinical benefit from treatment with ADCT-402. Following recovery to Grade 1 or to baseline Grade, treatment with ADCT-402 may resume at the Investigator's discretion.

Patients who resume treatment following a dose delay may, at the discretion of the Investigator, have their dose reduced by 1 dose level. If toxicity recurs at a severity that would mandate a dose delay, then the dose may be further reduced 1 dose level. If toxicity recurs at such level, then the patient is to be discontinued from treatment. Dose re-escalation is allowed at the Investigator's discretion, at maximum to the dose level the patient was initially assigned to.

Dose frequency may be adjusted according to individual patient response as described in Section 3.2.

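### Hematologic DLTs mature about 3 and 5 weeks after the 21-day DLT window closes, and no readable rule requires a late-confirmed event to be added to its dose level's count

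*Protocol*

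**What the plan says.** **Criterion.** Protocol 6.3.1 (repeated in the synopsis) has two hematologic criteria, both requiring less than 5% blasts. The first is Grade 3 or higher neutropenia or thrombocytopenia, or anemia of Grade 4, "with a hypocellular bone marrow lasting for 6 weeks or more after the start of a cycle, in the absence of residual leukemia". The second, for a normocellular marrow, is 8 weeks of pancytopenia of Grade 3 or higher.

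**Window.** The same section states: "The DLT observation period for dose-escalation will be 1 cycle". Section 5.4 identifies that period as Cycle 1 when it speaks of a "protocol-defined DLT after Cycle 1 (the defined DLT observation period"). The synopsis and 3.2 set a 21-day cycle; for the weekly schedule, "Patients will be given ADCT-402 QW on Days 1, 8 and 15 of each 3-week (21-day) treatment cycle". Cycle 1 is not held open for low counts: "Patients will receive the first 2 cycles of ADCT-402, irrespective of blood count recovery" (5.4).

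**Rules that rest on the window.** Under 3.2, if none of the first 3 patients has a DLT, "new patients may be entered at the next higher dose level"; the same applies after 1 of 3 followed by 0 of 3. The first QW cohort may not exceed the cumulative dose of the highest every-3-week (Q3W) level "at which 3 patients completed the DLT observation period without a DLT".

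**What happens to late DLTs.** Section 4.2.1 withdraws a patient with a DLT beyond Cycle 1, with a Sponsor exception for benefit, and 5.4 lets the Investigator suspend dosing. The Part 2 check in 3.2 applies the DLT criteria over the whole treatment period, with a trigger above 30%. The DESC reviews safety at least monthly and sets dose levels and the MTD (6.3.2).

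**The concern.** DLTs and the MTD are primary endpoints of Part 1 (7.2.1). A criterion that takes 6 or 8 weeks to satisfy cannot be confirmed in a 3-week window. A cohort can therefore be cleared, and a candidate QW starting dose identified, before any patient in it could have met the hematologic definition. If a patient meets it later, the protocol says what happens to that patient but not to the cohort's count. Two committees could apply the same text and reach different tallies for the same dose level. At stake is what a cleared cohort says about marrow tolerability, which matters for a drug whose DLT definition gives prolonged marrow aplasia its own criterion.

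**Working it through.** **Plan's own figure.** The documents give no probability for DLT detection. The only probability stated is in 7.3, for Part 2 cohorts of 10 at a 15% AE rate: 1 − 0.85^10 = 0.803, which matches the stated 80% when read as at least one AE. It does not bear on this point.

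**Timing, from the documents.**
- Window: 1 cycle × 21 days, closing on Day 21.
- 6-week criterion: Day 1 + 42 = Day 43, and 43 − 21 = 22 days after the window closes.
- 8-week criterion: Day 1 + 56 = Day 57, and 57 − 21 = 36 days after.
- First on-treatment marrow (4.1.2.1): within 6 days before Cycle 3 Day 1, so Days 37–42 if undelayed. Cellularity and blasts are not scheduled for assessment inside the window.
- Next scheduled marrow: before Cycle 5 Day 1 (1 + 4 × 21 = Day 85), so Days 79–84, or later.
- Edge case: 5.4 allows a dose delay of up to 21 days for non-DLT toxicity. If Cycle 1 were taken to run until Cycle 2 Day 1, it could last 21 + 21 = 42 days, just reaching the first criterion and not the second.
- Exposure before Day 43, undelayed: Q3W on Days 1 and 22 (2 doses); QW on Days 1, 8, 15, 22, 29 and 36 (6 doses).

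**Size, illustration only.** The probability that a level passes the 3+3 step is P = q³ + 3pq² × q³, where p is the DLT risk that registers and q = 1 − p. Every rate here is an assumption. Both criteria need less than 5% blasts, so the hematologic rate h cannot exceed the share of patients whose marrow clears. Taking clearing shares of 20% to 60% and aplasia in 10% to 50% of those gives h from 0.2 × 0.1 = 2% to 0.6 × 0.5 = 30%. The non-hematologic risk is set at 10%.
- Only in-window events counted: p = 0.10, P = 0.729 + 0.243 × 0.729 = 0.906.
- Late hematologic events counted, independent risks: p = 1 − 0.9(1 − h).
- Late events counted, full overlap of risks: p = max(0.10, h).
- Half of aplasia cases also cause an in-window non-hematologic DLT: in-window p = 1 − 0.9(1 − h/2), compared with the independent-risk column.

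| h | In-window only | Counted, independent | Counted, full overlap | In-window, half also register |
|---|---|---|---|---|
| 2% | 0.906 | 0.875 | 0.906 | not run |
| 5% | 0.906 | 0.824 | 0.906 | 0.867 |
| 10% | 0.906 | 0.730 | 0.906 | 0.824 |
| 20% | 0.906 | 0.536 | 0.709 | 0.730 |
| 30% | 0.906 | 0.360 | 0.494 | 0.632 |

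In the last scenario the gap to the counted figure is 0.043, 0.094, 0.194 and 0.272 at 5%, 10%, 20% and 30%. With a 5% non-hematologic risk the in-window figure is 0.973, against 0.952 to 0.425 counted; with 20% it is 0.709, against 0.674 to 0.248. The table assumes no DESC action and full follow-up to maturity. It also mixes exposure periods: h reflects Cycle 2 dosing, while the 10% is a one-cycle risk.

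**The case against.** The strongest reply is that the text can be read to do the right thing already. The clearance and MTD sentences in 3.2 carry no time limit of their own, and an event starting in Cycle 1 could be taken as a Cycle 1 DLT confirmed later by its duration. Escalation is permissive, and the protocol leaves the matter to the committee: "The number of dose levels will depend on the emergent toxicity profile of ADCT-402 and will be decided by the DESC". All of this is fair. It shows that late events may be counted, not that they must be. The MTD sentence also follows, by its own wording, from clearance rules placed directly after the one-cycle window.

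Other parts of the reply narrow the point:
- **QW start.** A reader might infer that the QW starting dose is chosen blind to marrow toxicity. Section 3.2 bases it on the safety and tolerability of patients treated on Q3W, makes the Q3W level a ceiling, and leaves implementation to the DESC under continuous monitoring. Later Q3W data are within that basis.
- **Patients leaving early.** A reader might infer that someone who stops treatment cytopenic on Day 30 can never be assessed, yet is kept as DLT-evaluable under 4.2.3 and 7.4. AEs are collected for up to 84 days after the last dose or until new anti-cancer treatment (6.3.3.2); after a single Day 1 dose that reaches Day 85, past both Day 43 and Day 57. Patients with 5% blasts or more cannot meet either criterion. The gap is confined to cleared-marrow patients with unresolved cytopenia whose follow-up ends first.
- **In-window consequences.** Grade 3 or higher non-hematologic consequences of aplasia can still register as DLTs.

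Figure 2, the escalation schematic, is not shown, so the absence of a rule is a statement about the readable text only.

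**Conclusion.** The timing mismatch is certain on the documents. Outside the Cycle 2 delay edge case, a hematologic DLT cannot be confirmed in the window that governs cohort clearance and that the QW rule cites. Late events have stated patient-level consequences, can count in Part 2, and may inform the DESC. What is missing is a requirement to add them to their dose level's count or to re-review the cohort.

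Two stronger conclusions are not supported. One is that hematologic toxicity cannot influence the MTD: the DESC provisions and the untimed MTD sentence say otherwise. The other is that a reported result is biased. SAP 3.3 records that the trial stopped before dose escalation was complete, SAP 4.8.1 only lists DLTs, and SAP section 4 plans no hypothesis tests. The point limits what cleared cohorts show about marrow tolerability.

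Only the day counts are document-based. The pass probabilities show that the gap is small if hematologic DLTs are rare and large only if they are common; they do not estimate either. The point merits a wording change because it concerns a primary-endpoint rule with two plausible readings.

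**What to change.** In Protocol 3.2 and 6.3.1, state that a hematologic event with onset in Cycle 1 counts toward its dose level's DLT tally, the MTD or recommended dose, and the choice of QW starting dose once it meets the 6- or 8-week criterion, even after Day 21. State that the DESC must re-review the cohort count when this happens. Escalation need not be held until Day 43 or Day 57. Whether 6 and 8 weeks are the right durations is for the sponsor's medical team.

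Secondary: add a note in 4.2.3 and 7.4 on patients with less than 5% blasts and unresolved cytopenia whose follow-up ends before the criterion can be assessed (consent withdrawal, death, loss to follow-up or new anti-cancer treatment), for example flagging them as not assessable for hematologic DLT. No SAP change is needed; a qualification date in the DLT listing would be optional.

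The cost is mainly operational. A count may change 3 to 5 weeks after clearance, possibly with the next level already open. A move from 0 of 3 to 1 of 3 can trigger the already planned expansion by up to 3 patients. Cycle 2 dosing complicates attribution, which the DESC must weigh. Confirming the 8-week criterion may need a clinically indicated marrow between the scheduled samples.

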6.3.2 Safety Oversight by the Dose-Escalation Steering Committee

A DESC will be responsible for safety monitoring and overall supervision of the study. Membership of the DESC will include:

- Medical monitor(s)/Pharmacovigilance representative(s) (Sponsor and/or designee)
- Investigator(s) from each participating site
- Biostatistician(s)
- Ad-hoc members (e.g., project manager, study coordinators, regulatory representatives, etc.)

ADCT-402-102 Protocol Amendment 3

In general, the DESC will make any substantial decisions regarding the conduct of the study, such as:

- Monitor the safety of the study and review its progress at monthly intervals or more frequent intervals as required.
- Determine dose levels to be administered and the MTD based on assessment of safety findings and determination of DLTs.
- Approve any amendments or administrative changes to the protocol, when required.
- Determine if it is appropriate to maintain a QW schedule, revert to a Q3W schedule, or test other dosing regimens.

Each DESC meeting and the decisions made will be documented in writing and provided to all participating DESC members and Investigators. Meeting documents may be submitted to IRBs/IECs or competent authorities according to institutional or local requirements.

The DESC will be maintained during Part 2 (expansion) of the study to continue to monitor and evaluate patient safety.

6.3.3 Adverse Events

6.3.3.1 Definitions of Adverse Events

The Investigator is responsible for reporting all AEs that are observed or reported during the study, regardless of their relationship to study drug or their clinical significance.

An AE is defined as any untoward medical occurrence in a patient enrolled into this study regardless of its causal relationship to study drug. Patients will be instructed to contact the Investigator at any time after assignment to the treatment group if any symptoms develop.

A treatment-emergent AE (TEAE) is defined as any event not present before exposure to study drug or any event already present that worsens in either intensity or frequency after exposure to study drug.

An SAE is defined as any event that results in death, is immediately life-threatening, requires inpatient hospitalization or prolongation of existing hospitalization, results in persistent or significant disability/incapacity, or is a congenital anomaly/birth defect. Hospitalization for elective procedures or for protocol compliance is not considered an SAE.

Important medical events that may not result in death, are life-threatening, or require hospitalization may be considered SAEs when, based upon appropriate medical judgment, the event may jeopardize the patient or may require medical or surgical intervention to prevent any of the outcomes listed in this definition. Examples of such medical events include allergic bronchospasm requiring intensive treatment in an emergency room or at home, blood dyscrasias

ADCT-402-102 Protocol Amendment 3

or convulsions that do not result in inpatient hospitalization, or the development of drug dependency or drug abuse.

6.3.3.2 Eliciting and Documenting Adverse Events

Adverse events will be assessed from the time the patient signs the ICF up to 84 days (12 weeks) days after the last dose of study drug or initiation of new anti-cancer treatment.

Any SAEs that occur > 84 days (12 weeks) after the last dose of study drug do not need to be reported unless the Investigator considers them to be related to study drug.

At every study visit, patients will be asked a standard non-leading question to elicit any medically related changes in their well-being. They will also be asked if they have been hospitalized, had any accidents, used any new medications, or changed concomitant medication regimens (both prescription and over-the-counter medications).

In addition to patient observations, AEs will be documented from any data collected on the AE page of the eCRF (e.g., clinically significant changes in laboratory values, physical examination, ECG changes, etc.) or identified from review of other documents that are relevant to patient safety.

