4.1.8 End of Treatment Visit

The following procedures will be performed within 30 days (+ 7 days) after study treatment discontinuation:

- Serum or urine pregnancy test.
- Physical examination including whole body skin assessment.
- Weight and vital signs.
- ECOG performance status.
- Hematology, coagulation panel, and biochemistry parameters.
- Urinalysis and sample collection for assessment of additional renal function studies.
- 12-lead ECG.
- Sample collection for central laboratory assessment of PK and ADA.
- Whole blood sample collection for central laboratory analysis of peripheral WBC populations and evaluation of CD19 and other CD markers (e.g., CD20, CD21, CD22).
- MNC) samples:
 - Whole blood (WB) sample collection with subsequent MNC isolation for retrospective central laboratory evaluation of CD19 and other CD markers (e.g., CD20, CD21, CD22).

ADCT-402-102 Protocol Amendment 3

- Collection of AE information.
- Collection of concomitant medication information.
- Bone marrow sample for disease assessment (see Section 4.1.2.1).

4.1.9 12-week Follow-up Visit

Each patient will have a sample taken for assessment of PK and ADA at 12 (± 1) weeks after their last dose of ADCT-402.

Blood Sample Collection and Adverse Event Monitoring During Long-Term Follow-up

For all patients, a PK and ADA blood sample collection will be performed 12 weeks (± 1 week) following the last dose of ADCT-402.

For all patients, collection of AEs and SAEs will continue for up to 84 days (12 weeks) after the last dose of study drug or initiation of new anti-cancer treatment (see Section 6.3.3.2).

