7.6 Statistical Analysis Methodology

7.6.1 Safety Analyses

7.6.1.1 Analyses of Adverse Events

An AE will be considered to be a TEAE if it begins or worsens on or after the patient's first study medication dose date and before the last dose date up to 84 days (12 weeks). Planned summaries of TEAEs will be detailed in the SAP and will include:

- All TEAEs.
- All serious TEAEs.
- All treatment-related TEAEs.
- All treatment-related serious TEAEs.
- All TEAEs resulting in study drug discontinuation.
- All DLTs

ADCT-402-102 Protocol Amendment 3

Other AE analyses of interest will be specified in the SAP.

The incidence of deaths and the primary cause of death will be summarized.

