- 19. 12-lead ECG: On Day 1 of Cycle 3 and subsequent cycles, a 12-lead ECG is to be performed before the start of ADCT-402 infusion.
- 20. Concomitant medications to include prescription or over-the-counter medication, herbal or naturopathic products within the 14 days prior to the Cycle 1, Day 1 visit, during the study and 30 days following the patient's last dose of ADCT-402.
- 21. Premedication to be performed if a CTCAE Grade 2 or higher infusion-related hypersensitivity reaction is observed in 1 patient at any time during Part 1 of the study. All subsequent patients must receive prophylactic treatment on Day 1 of each cycle thereafter to reduce the risk of hypersensitivity reaction (Section 5.2).
- 22. ADCT-402: Patients will receive a 1-hour IV infusion of ADCT-402, at escalating doses, each 3-week (21-day) cycle. If ADCT-402 is well tolerated after the first infusion, the infusion duration may be shortened to 30 minutes for subsequent infusions for that patient, at the Investigator's discretion. Variations in infusion times due to minor differences in IV bag overfill/underfill and the institution's procedure for flushing chemotherapy lines will not result in protocol deviation. The IP window is +15 minutes.
- 23. For all patients, collection of AEs and SAEs will continue for up to 12 weeks (84 days) after the last dose of study drug or initiation of new anti-cancer treatment. Any SAEs that occur more than 84 days after the last dose of study drug do not need to be reported unless the Investigator considers the event to be related to study drug.
- 24. After documentation of disease progression or start of new anti-cancer treatment, patients will be contacted by telephone approximately every 12 weeks for up to 12 months after the last dose of study drug to collect survival information.
- 25. Information on anti-cancer treatment initiated after discontinuation of ADCT-402 to be recorded in the eCRF.

Date of Protocol: 19 April 2017 Page 77 Page 77

Table 7. Schedule of Study Procedures: Weekly (QW) Dosing

Procedure	Screen			Cycle 1					Cycle 2				Cycles 3 ntil PD/D		EOT 30 (+7)	12 Week Follow-	Follow- Up
rrocedure	Scr	D1 ±3d	D2 ¹	D3& ²	D8	D15	D1 ±3d	D2 ¹	D3&5 ²	D8 ±2d	D15 ±2d	D1 ±3d	D8 ±2d	D15 ±2d	days ³	Up Visit (± 1) week ⁴	12 (± 1) week
Informed consent	X																
Demography	X																
Medical history ⁵	X																
Serum or urine β-HCG pregnancy test	X	X ⁶													X		
Physical examination ⁷	X	X			X	X	X			X	X	X			X		

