### **4.8.2 Adverse Events, Serious Adverse Events, and Deaths**

#### **4.8.2.1 Analyses of adverse events**

The primary focus of adverse event reporting will be on the TEAEs. A TEAE is defined as an adverse event (AE) that occurs or worsens in the period from the first dose of study drug up to 84 days after the last dose of study drug, or start of new anti-cancer therapy, whichever is earlier.

If an AE date/time of onset (occurrence, worsening, or becoming serious) is incomplete, an imputation algorithm will be used to classify the AE as pre-treatment, TEAE, or post-treatment. For example, if only the day of the AE onset is missing, the year and month will be compared with the first dose and 84 days after the last dose of study drug, or start of new anti-cancer therapy, whichever is earlier. And if the month and day of the AE onset are missing, the year will be compared with the first dose and 84 days after the last dose of study drug, or start of new anti-cancer therapy, whichever is earlier. The algorithm for imputing TEAE will be conservative and will classify an AE as a treatment emergent unless there is definitive information to determine it is non-TEAEs.

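### A drug-related SAE between the start of new anti-cancer therapy and day 84 has no explicit reporting rule, and the SAP keeps it out of every TEAE table although protocol 7.6.1.1 would count it

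*Protocol*

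**What the plan says.** **Collection.** Protocol 6.3.3.2 follows AEs from consent to 84 "days after the last dose of study drug or initiation of new anti-cancer treatment". Section 4.1.9 and footnote 23 of Tables 5 and 7 use the same construction for AEs and SAEs together: "up to 84 days (12 weeks) after the last dose of study drug or initiation of new anti-cancer treatment". None of these places says which end point governs when new treatment begins before day 84.

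**Late SAEs.** Section 6.3.3.2 adds that SAEs more than 84 days after last dose "do not need to be reported unless the Investigator considers them to be related to study drug". Footnote 23 repeats the rule. The threshold is day 84 alone, and new therapy is not mentioned.

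**General duties.** Section 6.3.3.1 states: "The Investigator is responsible for reporting all AEs that are observed or reported during the study, regardless of their relationship to study drug". Section 6.3.3.3 sends any event meeting the SAE criteria to the CRO within 24 hours of the site learning of it. Neither section makes an exception for new therapy.

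**TEAE window.** Protocol 7.6.1.1 bounds it by the "first study medication dose date and before the last dose date up to 84 days", read here as 84 days after last dose, with no cut at new therapy. SAP 4.8.2.1 runs it "up to 84 days after the last dose of study drug, or start of new anti-cancer therapy, whichever is earlier".

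**Outputs.** Every AE summary in SAP 4.8.2.1 is a TEAE summary. The same section lists all AEs and all SAEs, including non-TEAEs. SAP 4.8.2.2 summarises reasons for all deaths.

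**The concern.** Safety and tolerability is a primary objective. After early termination the SAP only lists efficacy and DLT data, so the TEAE tables carry most of the summarised safety evidence. A patient who stops ADCT-402 and moves quickly to another treatment has the shortest counted window. A later event that the investigator attributes to ADCT-402 is then missing from the incidence figures.

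The explicit rules are also uneven. A related SAE after day 84 is expressly reportable. The same event before day 84, in a patient already on new therapy, is not expressly addressed.

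Finally, protocol and SAP give different TEAE windows. SAP 3.3 attributes its modified analyses to early termination and refers to the later sections for detail. Neither SAP 3.3 nor SAP 4.8.2.1 identifies the cut at new therapy as a change from protocol 7.6.1.1.

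**Working it through.** No figure in the plan bears on this point, so the check is a reconciliation of texts plus a simple measure of the window removed.

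**1. Where collection ends.** Count days from last dose and take a patient who starts new therapy on day 14 (an assumed value).
- If the *or* in 6.3.3.2 means the earlier event, collection ends on day 14.
- If it means 84 days after last dose, collection ends on day 84.
- If the 84 days can also be counted from new treatment, collection could run to day 14 + 84 = 98.

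The protocol wording allows all three. Only the SAP chooses the first, and only for the analysis window.

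**2. One event under each rule.** Same patient, with an SAE judged related to ADCT-402:

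| Rule | Onset day 40 | Onset day 100 |
|---|---|---|
| Explicit related-SAE rule (6.3.3.2, footnote 23) | not addressed | reportable |
| General duties (6.3.3.1, 6.3.3.3) | reportable, if within the study | reportable, if within the study |
| TEAE, protocol 7.6.1.1 (to day 84) | yes, 40 < 84 | no |
| TEAE, SAP 4.8.2.1 (to the earlier of 84 and 14, so day 14) | no, 40 > 14 | no |
| SAP listings of all AEs and SAEs | yes, if recorded | yes, if recorded |

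The two TEAE definitions disagree in the day-40 column, and that column has no explicit reporting rule.

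**3. Share of the window removed.** With new therapy starting on day s, the SAP drops (84 − s)/84 of that patient's post-treatment window. The documents do not give s, so this is an assumed range:

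| s (days) | Days dropped | Share |
|---|---|---|
| 14 | 70 | 83% |
| 21 | 63 | 75% |
| 30 | 54 | 64% |
| 42 | 42 | 50% |
| 60 | 24 | 29% |

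These are shares of calendar time, not of events or patients. No late-event rate is given from which to convert them.

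**4. Consistency with the rest of the SAP.** SAP 4.8.2.1 treats an event with an incomplete onset date as treatment-emergent unless there is definite evidence otherwise. SAP 6.1.1 counts missing causality as related. Leaving out an event that the investigator has actively judged related runs against both conventions.

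**The case against.** A reader might infer that sites have no duty to report these SAEs and that the events are lost. The documents do not support that:
- Sections 6.3.3.1 and 6.3.3.3 impose general duties without exception for new therapy, and section 4.2 runs participation through follow-up.
- Section 6.3.3.2 waives SAEs only after day 84, which implies that earlier ones stay reportable.
- Tables 5 and 7 schedule AE collection at the 12-week visit, where new-treatment information is also recorded.
- Events that are recorded remain in the listings, and SAP 4.7.2 lists subsequent therapy with start dates, so they can be identified by hand.

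All of this stands. It leaves a conflict in the text and an omission from the tables. The general duty is also not watertight. Its scope is the study, which section 10.3 ends at the last EOT visit of the last patient. Section 4.1.10 gives survival information as the purpose of contact after new therapy starts.

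It can be said that the two halves of the point cancel. If collection stops at new therapy, the SAP cut merely matches it. If collection continues, there is no reporting gap. But the documents do not settle which is true, and the tables omit the event either way.

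Ending the TEAE window at new therapy also has a sound purpose, since it limits confounding by that therapy. This justifies the cut for unrelated events. It is weaker for events attributed to ADCT-402.

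Nor do the 6- and 8-week hematologic DLT criteria show that late onset is expected. They describe how long cytopenia persists, and a cytopenia that begins before new therapy is already a TEAE.

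**Conclusion.** The point holds as an ambiguity in the protocol and a discrepancy between protocol and SAP. A related SAE with onset after new therapy and by day 84 has no explicit rule, and the relevant protocol sections do not sit together. The SAP removes it from every TEAE table, while protocol 7.6.1.1, read as 84 days after last dose, would include it. Among the AE and death outputs it is left to the listings, and to the all-deaths summary if fatal.

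The number of such events is unknown. The 83% to 29% range rests on assumed start days of 14 to 60, and measures time for an affected patient only. The analysis is descriptive, so no test or error rate is affected. The consequence is possible undercounting in the main safety summary, which is cheap to correct.

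**What to change.** 1. **Protocol 6.3.3.2, 4.1.9 and footnote 23 of Tables 5 and 7:** state that SAEs judged by the investigator to be related to ADCT-402 are reported whenever they occur, including after new anti-cancer treatment has begun. This is one sentence, repeated in each place.
2. **SAP 4.8.2.1:** keep the cut at new therapy for unrelated events. Also count AEs assessed as related with onset within 84 days of last dose regardless of new therapy, flagged or in a separate row.
3. **SAP 3.3:** name the departure from protocol 7.6.1.1.

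The cost is some events whose attribution is shared with the next therapy, and different observation windows for related and unrelated events. A separate row keeps both visible. No visit is added, because the 12-week PK and ADA visit already applies to all patients.

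Because the trial ended early, the protocol sentence is unlikely to recover data that were not collected. The SAP change still works on whatever was recorded. If some sites stopped collecting at new therapy, the added row should be read as a minimum count.
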